16.12.8. Pharmacokinetic Tables

Pharma	Pharmacokinetic: Tables							
No.	Population	IDSL / TST ID / Example Shell	Title	Programming Notes	Deliverable			
PK Plas	sma Concentra	tion						
4.1.	РК	PKCT1	Summary of Plasma GSK2330811 Concentration-Time Data (ng/mL)	Add footnotes " Note: No. of subjects with results below the lower limit of quantification, assigned 0 (LLQ=100 ng/mL). SD is set to missing if No. Imputed/n > 0.3 Samples from Day 14 – Day 84 are taken at trough (2 weeks after dosing)."	DEC, IA1, IA2, Adhoc DRC, SAC			

16.12.9. Pharmacokinetic Figures

Pharmacokinetic: Figures						
No.	Population	IDSL / TST ID / Example Shell	Title	Programming Notes	Deliverable	
PK Plas	sma Concentra	tion				
4.1.	PK	PKCF1P	Individual GSK2330811 Plasma Concentration-Time Plot by Subject (Linear and Semi-Log)	Footnote for all PK and PK/PD figures: Note: No. of subjects with results below the lower limit of quantification, assigned 0 (LLQ=100 ng/mL). Samples from Day 14 – Day 84 are taken at trough (2 weeks after dosing). Use actual time (days) as x axis (where days is a continuous variable)	DEC ^[1] , SAC	
4.2.	РК	PKCF1P	Individual GSK2330811 Plasma Concentration-Time Plot by Treatment (Linear and Semi-Log)	Use actual time (days) as x axis (where days is a continuous variable) [difference between this and 4.1 is that all profiles will be on one page for each treatment group] Note: No. of subjects with results below the lower limit of quantification, assigned 0 (LLQ=100 ng/mL). Samples from Day 14 – Day 84 are taken at trough (2 weeks after dosing).	IA1 ^[1] , IA2 ^[1] , Adhoc DRC, SAC	
4.3.	PK	PKCF4	Mean (\pm SD) Plasma GSK2330811 Concentration-Time Plots by Treatment (Linear and Semi-log)	Use planned time (days) as x axis (where days is a continuous variable)	IA1, IA2, SAC	
4.4.	РК	PKCF5	Median (Range) Plasma GSK2330811 Concentration-Time Plots by Treatment (Linear and Semi-log)	the lower limit of quantification, assigned 0 (LLQ=100 ng/mL). Samples from Day 14 – Day 84 are taken at trough (2 weeks after dosing).	SAC	

201247

Pharmacokinetic: Figures							
No.	Population	IDSL / TST ID / Example Shell	Title	Programming Notes	Deliverable		
4.5.	РК	201246/adhoc/ Figure 4.9	Mean (±SD) Plasma GSK2330811 Concentration-Time Plots grouped by Treatment (Linear and Semi-log)	As Figure 4.3 but on a single page , grouped by treatment. Add footnote Note: No. of subjects with results below the lower limit of quantification, assigned 0 (LLQ=100 ng/mL). Samples from Day 14 – Day 84 are taken at trough (2 weeks after dosing).	IA1, IA2, Adhoc DRC, SAC		
4.6.	РК	PK_F1	Scatter Plot of Individual Measured Steady State Concentration vs Baseline Body Weight	Panel by treatment group and grouped by individual subjects. X-axis Label: Body Weight (kg) Y-axis Label: Measured Steady State Concentration (ng/mL)	Adhoc DRC, SAC		
4.7.	РК	PK_F1	Scatter Plot of Individual Platelet Nadirs as Percentage Change from Baseline vs Measured Highest Concentration	Panel by treatment group and grouped by individual subjects. X-axis Label: Measure Highest Concentration (ng/mL) Y-axis Label: Percentage Change from Baseline of Platelet Nadirs	Adhoc DRC, SAC		
4.8.	РК	PK_F1	Scatter Plot of Individual Hemoglobin Nadirs as Percentage Change from Baseline vs Measured Highest Concentration	Panel by treatment group and grouped by individual subjects. X-axis Label: Measure Highest Concentration (ng/mL) Y-axis Label: Percentage Change from Baseline of Hemoglobin Nadirs	SAC		
Notes:							

1: Individual figure(s) will be produced for interim but may not be shared with the study team. Justification: DRCs follow the principle of presenting summary data where possible to reduce the degree of unblinding, so this output will only be presented if necessary.

16.12.10. Pharmacokinetic Population (PopPK) Tables

Pharmacokinetic Population (POPPK): Tables						
No.	Population	IDSL / Example Shell	Title	Programming Notes	Deliverable [Priority]	
PopPK						
5.1.	РК	NA	Summary of Derived Plasma GSK2330811 Pharmacokinetic Parameters from Population PK model	Produced by CPMS Note: this table will contain the parameters from the Population PK analysis (which already summarise all the subjects). It will NOT be a summary of the individual subject's parameters. Optional Footnote: Parameters estimated from study 201246 OR Parameters estimated from observed data and data from 201246.	IA1 , SAC	
5.2.	PK	NA	Predicted median (95%CI) vs Observed Mean (SE) plasma GSK2330811 concentration	Produced by CPMS	DEC, IA1 , SAC	

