16.10.3. Model Development

A population PK/PD model for SC single dose of GSK2330811 in healthy volunteers was developed [Reid J, 2018] and will be the starting point for the population PK/PD analysis.

Individual parameters (empirical Bayes estimates) will be derived applying the HV popPKPD model to the repeat dose in dcSSc dataset with the MAXEVAL=0 option, if \$EST METHOD=1, or with the EONLY=1 option, if \$EST METHOD=IMP. If the corresponding model diagnostics indicate that the HV popPKPD model is appropriate to represent the dcSSc PKPD data, then these individual parameters for the dcSSc population will be considered adequate to characterise the PK/PD.

201247

If the parameter set of the HV popPKPD model applied to the dcSSc data set results in substantial bias or if a further exploration of the covariate effect in the dcSSc population is deemed necessary, the parameters of the HV popPKPD model will be re-estimated for the dcSSc PK/PD data alone and/or for a pooled HV (study 201246, study 208564 cohort 1) /dcSSc (study 201247) data set. If a pooled analysis is deemed necessary, it will be performed as a separate analysis and reported separately.

201247

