16.12.11. Pharmacokinetic Population (PopPK) Figures

Pharmacokinetic Population (POPPK): Figures							
No.	Population	IDSL / Example Shell	Title	Programming Notes	Deliverable [Priority]		
PopPK		-		-	-		
5.1.	PK	NA	Predicted Median (95% CI) vs Mean (SE) of Plasma GSK2330811	Produced by CPMS At each dose level Footnote: CI = Confidence Interval	DEC, IA1, IA2, Adhoc DRC, SAC		
5.2.	PK	NA	Predicted Median (95% PI) vs Individual Observed Values of GSK2330811	Produced by CPMS At each dose level Note: May not be shared with the study team at interim analyses. Footnote: PI = Prediction Interval	DEC ^[1] , IA1 ^[1] SAC		
5.3.	PK	NA	Predicted Median (95% PI) vs Observed Range of GSK2330811	Produced by CPMS At each dose level Footnote: PI = Prediction Interval	DEC, IA1, IA2, Adhoc DRC, SAC		
Notes: 1: Indivi	dual figure(s) wi	Il be produced for i	nterim but may not be shared. Justification: DRCs follow the princip	e of presenting summary data where po	ossible to reduce		

the degree of unblinding, so this output will only be presented if necessary.

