16.12.15. Pharmacokinetic / Pharmacodynamic Figures

Pharmacokinetic / Pharmacodynamic: Figures							
No.	Population	IDSL / Example Shell	Title	Programming Notes	Deliverable [Priority]		
PK/PD							
7.1.	IA1, IA2, Adhoc DRC: Safety DEC, SAC: Per Protocol	NA	Predicted median (95% CI) vs Mean (SE) Total OSM	CPMS to produce this output	DEC, IA1, IA2, Adhoc DRC, SAC		
7.2.	IA1: Safety DEC, SAC: Per Protocol	NA	Predicted target engagement over time	CPMS to produce this output	IA1, SAC		
7.3.	IA1, IA2, Adhoc DRC: Safety DEC, SAC: Per Protocol	NA	Predicted median and (95% PI) vs Observed range of Total OSM	CPMS to produce this output	DEC, IA1, IA2, Adhoc DRC, SAC		
7.4.	IA1: Safety DEC, SAC: Per Protocol	NA	Predicted median (95% PI) vs Observed Total OSM	CPMS to produce this output Note: Shows individual data points, might not be shown to study team at interim.	DEC, IA1, SAC		

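### Four predicted-versus-observed displays set a predicted median against an observed mean, so a correct model can look as if it under-predicts, mainly at the late follow-up visits

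*SAP*

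**What the plan says.** Four displays produced by the modelling group pair a predicted median and 95% CI with an observed mean and SE:

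- Table 5.2 (SAP 16.12.10): "Predicted median (95%CI) vs Observed Mean (SE) plasma GSK2330811 concentration"; planned for the dose-escalation review, IA1 and the final analysis.
- Figure 5.1 (SAP 16.12.11): "Predicted Median (95% CI) vs Mean (SE) of Plasma GSK2330811"; planned for dose escalation, IA1, IA2, the ad hoc committee review and the final analysis.
- Table 7.2 (SAP 16.12.14) and Figure 7.1 (SAP 16.12.15): both titled "Predicted median (95% CI) vs Mean (SE) Total OSM".

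The SAP does not say which mean is meant or why it is set against a median. For plasma concentrations, SAP 16.5.2 points to the same reporting principle that it cites for normally distributed data and sets non-quantifiable values to zero. Both point to an arithmetic mean. For total OSM the position is open: Table 6.2 summarises it after log transformation, while Figure 6.3 plots a mean with SD without naming the type.

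Other displays avoid the problem. Figure 5.2 is "Predicted Median (95% PI) vs Individual Observed Values of GSK2330811", Figure 5.3 is "Predicted Median (95% PI) vs Observed Range of GSK2330811", Figure 7.3 is "Predicted median and (95% PI) vs Observed range of Total OSM", and Figure 7.4 shows the observed total OSM data points. Figures 4.4 and 6.4 plot observed medians, with no prediction overlaid.

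**The concern.** A median and an arithmetic mean are different targets. When concentrations are right-skewed, a model that reproduces the whole distribution exactly still has a predicted median below the observed mean. The discrepancy runs one way and does not shrink as the sample grows. A larger sample only narrows the SE and makes the discrepancy look more convincing.

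These four are the only listed displays that set a predicted centre against an observed central summary, so a reader asking whether the model is centred correctly will turn to them. SAP 16.10.3 has the healthy-volunteer model re-estimated or kept according to a judgement without a numerical threshold ("If the parameter set of the HV popPKPD model applied to the dcSSc data set results in substantial bias"). At stake is a misleading impression of under-prediction in the report.

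**Working it through.** The SAP gives no figure for this comparison, so the size has to be derived.

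**Inputs.** Protocol 5.5: CL/F 14.1 mL/hr (95% CI 12.7 to 15.6), V/F 11.5 L (95% CI 10.2 to 13.1), and predicted steady-state AUC 21300 ug.h/mL and Cmax 68.2 ug/mL at 300 mg every other week. Protocol 3.2: 30 participants exposed in the first human study. Protocol Table 3: 3 active participants in cohort 1 and 15 in cohort 2. SAP 16.9.1: LLQ 100 ng/mL.

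**Anchor.** 300 mg / 14.1 mL/hr = 21277 ug.h/mL, which reproduces the stated 21300. Half-life = ln 2 × 11.5 L / 0.0141 L/hr = 565 hr = 23.6 days, inside the stated 19 to 25.

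**Variability.** The documents give no between-participant SD. Assuming SE = SD/√30 on the log scale, SD = [ln(upper/lower) / (2 × 1.96)] × √30:

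- CL/F: ln(15.6/12.7) = 0.206, so SD = 0.29.
- V/F: ln(13.1/10.2) = 0.250, so SD = 0.35.

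**Closed form.** For log-normal data, mean/median = √(1 + CV²). This gives 1.04 at CV 30%, 1.12 at 50%, 1.28 at 80% and 1.41 at 100%.

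**Plasma simulation.** One-compartment model with first-order absorption, the absorption rate set to give Cmax 68.2 ug/mL, six doses of 300 mg at two-week intervals, independent log-normal CL/F and V/F with the SDs above, no residual error, and values below LLQ set to 0. The model is exactly correct by construction. The last two columns use n = 15.

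| Visit | Mean / median | Mean − SE above true median | Mean + SE below true median |
|---|---|---|---|
| Day 15 to Day 85 | 1.02 to 1.03 | 24 to 26% | 10 to 11% |
| Day 113 | 1.04 | 24% | 12% |
| Day 155 | 1.28 | 49% | 4% |
| Day 197 | 1.83 | 72% | 1% |

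Setting non-quantifiable values to zero hardly matters. About 10% fall below LLQ at Day 197, and the ratio there moves only from 1.826 to 1.824. The observed median of 15 lies above the true median in 50% of samples at every visit, so the matched comparison has no direction.

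**Sensitivity.**

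- Adding 15% residual error gives 1.04 at troughs, 1.06 at Day 113, 1.30 at Day 155 and 1.84 at Day 197.
- SDs of 0.4 with 20% residual error give 1.06 to 1.07, 1.13, 1.52 and 2.41.
- A correlation of 0.5 between log CL/F and log V/F (assumed; none is stated) gives 1.04 at troughs, 1.05 at Day 113, 1.18 at Day 155 and 1.46 at Day 197.
- With n = 3, as in cohort 1, the mean exceeds the true median in about 54 to 55% of samples at on-treatment troughs, close to a coin toss.

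**Total OSM.** No CV is stated. For assumed CVs of 30% to 100% the closed form gives a gap of 4% to 41%, if the mean is arithmetic. If it is a geometric mean there is no gap for log-normal data.

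**The case against.** The strongest reply is that little turns on these four displays. Several parts of it stand.

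- A reader might infer that these displays decide whether the healthy-volunteer model is kept. SAP 16.10.3 refers only to unnamed model diagnostics and cites none of the four. Figures 5.3 and 7.3, which lack the mismatch, are planned for the same reviews as Figures 5.1 and 7.1.
- A reader might also infer that the interim judgement of target engagement is biased. SAP 3.2 frames that judgement in terms of baseline total OSM and mean target engagement. Engagement is derived from free OSM, is presented as a predicted value (SAP 16.6.5), and has its own Figure 7.2. The skewness argument is not shown to carry over to it. The interims also appear to be past: treatment was complete by April 2020 and this SAP is dated August 2020.
- To say that a correct model will look low is too strong. On treatment the plasma gap is a few per cent.
- The table treats the prediction as a point, but the display gives it a 95% CI. With an illustrative upper limit 10% above the median (about the relative width of the CL/F interval), mean − SE clears that limit in under 2% of samples at Day 15 to Day 85 and 7% at Day 113, but still in 33% at Day 155 and 63% at Day 197. The real interval is not specified and could be wider at late visits.
- The difference between a 95% CI and an SE is labelled in the titles. Matching them is a preference.

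What does not stand is that the other figures make the comparison harmless. Those with prediction intervals address spread, and those with observed medians carry no prediction.

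**Conclusion.** The mismatch is in the current text and its direction is known for right-skewed data: a correct model can look as if it under-predicts. For plasma the expected gap is about 2 to 4% on treatment and at Day 113, about 28% at Day 155 and about 80% at Day 197. These figures rest on a back-calculated SD, a one-compartment model, independent CL/F and V/F, and the inference that the mean is arithmetic. With a correlation of 0.5 the late gaps drop to about 18% and 46%, still too large to ignore. For total OSM the size cannot be given, because the documents state neither the type of mean nor the CV.

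The documents do not support a claim that the adequacy decision or the interim engagement decision was pushed one way. The severity is minor.

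**What to change.** In Tables 5.2 and 7.2 and Figures 5.1 and 7.1, set the predicted median against the observed median, or the predicted mean against the observed mean, and name the summary in the title or footnote. A geometric mean is a fair alternative to the observed median where no values are set to zero. That suits total OSM, whose values below LLQ are set to half the LLQ in the SAP's OSM tables, but not late plasma samples. Using the same type of interval on both sides is optional.

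The cost is four display titles and shells. No new data are needed, and the observed medians are already computed for Figures 4.4 and 6.4. Only the final-analysis outputs appear still open to change.

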16.12.11. Pharmacokinetic Population (PopPK) Figures

Pharmacokinetic Population (POPPK): Figures							
No.	Population	IDSL / Example Shell	Title	Programming Notes	Deliverable [Priority]		
PopPK		-		-	-		
5.1.	PK	NA	Predicted Median (95% CI) vs Mean (SE) of Plasma GSK2330811	Produced by CPMS At each dose level Footnote: CI = Confidence Interval	DEC, IA1, IA2, Adhoc DRC, SAC		
5.2.	PK	NA	Predicted Median (95% PI) vs Individual Observed Values of GSK2330811	Produced by CPMS At each dose level Note: May not be shared with the study team at interim analyses. Footnote: PI = Prediction Interval	DEC ^[1] , IA1 ^[1] SAC		
5.3.	PK	NA	Predicted Median (95% PI) vs Observed Range of GSK2330811	Produced by CPMS At each dose level Footnote: PI = Prediction Interval	DEC, IA1, IA2, Adhoc DRC, SAC		
Notes: 1: Indivi	dual figure(s) wi	Il be produced for i	nterim but may not be shared. Justification: DRCs follow the princip	e of presenting summary data where po	ossible to reduce		

the degree of unblinding, so this output will only be presented if necessary.

16.12.12. Pharmacodynamic Tables

Pharmacodynamic Tables						
No.	Population	IDSL / TST ID / Example Shell	Title	Programming Notes	Deliverable	
Serum	OSM					
6.1.	Adhoc DRC: Safety SAC: Per Protocol	PD_T1	Summary of Log Transformed Serum Level of Free OSM (pg/mL)		Adhoc DRC, SAC	
6.2.	IA1, IA2, Adhoc DRC: Safety SAC: Per Protocol	PD_T1	Summary of Log Transformed Serum Level of Total OSM (pg/mL)	Add number imputed, Add footnote: [1] No. of subjects with results below the lower limit of quantification, assigned to half of the lower limit of quantification (LLQ = 1.45	IA1, IA2, Adhoc DRC, SAC	
6.3.	Per Protocol	PD_T1	Summary of Ratio of Serum Level of Free OSM (pg/mL) to Baseline	pg/ml)	SAC	
6.4.	IA1, IA2: Safety SAC: Per Protocol	PD_T1	Summary of Ratio of Serum Level of Total OSM (pg/mL) to Baseline		IA1, IA2, SAC	
Notes: V	Vill be produced	l for interim but ma	y not be shared due to small sample size being potentially unblindin	g.		

16.12.13. Pharmacodynamic Figures

Pharma	Pharmacodynamic: Figures							
No.	Population	IDSL / TST ID / Example Shell	Title	Programming Notes	Deliverable			
Serum	OSM							
6.1.	IA1: Safety SAC: Per Protocol	PKCF1P	Individual Serum Level of Free OSM Concentration-Time Plot by Treatment (Linear and Semi-Log)	Add LLQ reference line Page by treatment Add Footnote to indicate amount of imputed data. Add footnote: [1] No. of subjects with results below the lower limit of quantification, assigned to half of the lower limit of quantification (LLQ = 1.45 pg/ml) Use actual time (days) as x axis (where days is a continuous variable) Note: May not be shared with study team at interim.	IA1 ^[1] , SAC			
6.2.	IA1: Safety SAC: Per Protocol	PKCF1P	Individual Serum Level of Total OSM Concentration-Time Plot by Treatment (Linear and Semi-Log)	Add LLQ reference line. Conditionally add ULQ reference line Page by treatment Add footnote: [1] No. of subjects with results below the lower limit of quantification, assigned to half of the lower limit of quantification (LLQ = 1.45 pg/ml) Use actual time (days) as x axis (where days is a continuous variable) Note: May not be shared with study team at interim. Add Footnote to indicate amount of imputed data.	IA1 ^[1] , SAC			

Pharmacodynamic: Figures								
No.	Population	IDSL / TST ID / Example Shell	Title	Programming Notes	Deliverable			
6.3.	IA1, IA2: Safety SAC: Per Protocol	201246/adhoc/ Figure 5.19	Mean (±SD) Serum Level of Total OSM Concentration-Time Plots grouped by Treatment (Linear and Semi-log)	Add LLQ reference line Conditionally add ULQ reference line Use planned time (days) as x axis (where days is a continuous variable)	IA1, IA2, SAC			
6.4.	IA1, IA2: Safety SAC: Per Protocol	201246/adhoc/ Figure 5.19	Median (Range) Serum Level of Total OSM Concentration-Time Plots grouped by Treatment (Linear and Semi-log)		IA1, IA2, SAC			
Three p	anel PK/PD/Ha	ematology plots						
6.5.	PK	201246/Final/ Figure 6.9	Median Plasma GSK2330811 Concentration, Median Serum Level of Total OSM Concentration and Median Platelet Count Over Time by Treatment Group	Page by treatment group	SAC			
6.6.	PP	201246/Final/ Figure 6.9 / 6.20	Median Serum Level of Total OSM Concentration, Median Haemoglobin and Median Reticulocytes by Treatment Group,	Title of each panel to include endpoint and units, short form endpoint on y axis	SAC			
Notes: 1: Indi reduce t	Notes: 1: Individual figure(s) will be produced for interim but may not be shared. Justification: DRCs follow the principle of presenting summary data where possible to reduce the degree of unblinding, so this output will only be presented if necessary.							

16.12.14. Pharmacokinetic / Pharmacodynamic Tables

Pharmacokinetic / Pharmacodynamic: Tables								
No.	Population	IDSL / Example Shell	Title	Programming Notes	Deliverable [Priority]			
PK/PD								
7.1.	IA1: Safety SAC: Per Protocol	NA	Parameters from Target Engagement PK/PD Model, [for specify model] Model.	CPMS to produce this output if PK/PD model is developed for the reporting effort.	IA1, SAC			
7.2.	IA1: Safety SAC: Per Protocol	NA	Predicted median (95% CI) vs Mean (SE) Total OSM	CPMS to produce this	IA1, SAC			

201247

16.12.15. Pharmacokinetic / Pharmacodynamic Figures

Pharmacokinetic / Pharmacodynamic: Figures							
No.	Population	IDSL / Example Shell	Title	Programming Notes	Deliverable [Priority]		
PK/PD							
7.1.	IA1, IA2, Adhoc DRC: Safety DEC, SAC: Per Protocol	NA	Predicted median (95% CI) vs Mean (SE) Total OSM	CPMS to produce this output	DEC, IA1, IA2, Adhoc DRC, SAC		
7.2.	IA1: Safety DEC, SAC: Per Protocol	NA	Predicted target engagement over time	CPMS to produce this output	IA1, SAC		
7.3.	IA1, IA2, Adhoc DRC: Safety DEC, SAC: Per Protocol	NA	Predicted median and (95% PI) vs Observed range of Total OSM	CPMS to produce this output	DEC, IA1, IA2, Adhoc DRC, SAC		
7.4.	IA1: Safety DEC, SAC: Per Protocol	NA	Predicted median (95% PI) vs Observed Total OSM	CPMS to produce this output Note: Shows individual data points, might not be shown to study team at interim.	DEC, IA1, SAC		

16.12.16. Biomarker Tables

Biomarker: Tables									
No.	Population	IDSL / Example Shell	Title	Programming Notes	Deliverable [Priority]				
Systemic biomarkers									
8.1	Safety	BIO_T1	Summary of Baseline Levels of Systemic Biomarkers	Baseline values only No treatment groups. Exclude C1M results using mouse hybridoma cell line as small sample size may be unblinding. Add footnote 'Note: C1M assay changed during the study. C1M results not presented for samples analysed using the old C1M (denoted C1M*) kit due to small sample size and potential unblinding. New C1M kit denoted as C1M+.	IA2				
8.2	Per Protocol	BIO_T2	Summary of Systemic Biomarkers	By biomarker, by treatment ordered by endpoint type (Inflammation, Fibrosis,	SAC				
8.3	Per Protocol	BIO_T2	Summary of the Ratio to Baseline in Systemic Biomarkers	Vascular) Note: No. of subjects with results below the lower limit of quantification, assigned to half of the lower limit of quantification. Note: C1M assay changed during the study. Results using old kit denoted as C1M* and new kit denoted as C1M+. For only ratio to baseline table, add Fold change.	SAC				

Biomarker: Tables									
No.	Population	IDSL / Example Shell	Title	Programming Notes	Deliverable [Priority]				
8.4	Per Protocol	BIO_T3	Analysis of Systemic Biomarkers	For endpoints as specified in Section 13.1.5.	SAC				
Skin Histology biomarkers									
8.5	Per Protocol	BIO_T2	Summary of Alpha SMA Results	Include both sufficient and insufficient tissue samples	SAC				
8.6	Per Protocol	BIO_T2	Summary of Alpha SMA Results Excluding Insufficient Tissue Samples		SAC				
8.7	Per Protocol	BIO_T2	Summary of the Ratio to Baseline in Alpha SMA Results at Day 85 Excluding Insufficient Tissue Samples	Do not include Analysis visit column.	SAC				
8.8	Per Protocol	BIO_T7	Analysis of the Ratio to Baseline in Alpha SMA Results at Day 85 Excluding Insufficient Tissue Samples	For endpoints as specified in Section 13.1.5.	SAC				
Skin Gene Expression RNA Sequencing									
8.9	Per Protocol	BIO_T8	Summary of mRNA Gene Expression Results: Individual Genes of Interest		SAC				
8.10	Per Protocol	BIO_T9	Summary of the Ratio to Baseline in mRNA Gene Expression Results at Day 85: Individual Genes of Interest	By gene, by treatment.	SAC				
8.11	Per Protocol	BIO_T7	Analysis of the Ratio to Baseline in mRNA Gene Expression Results at Day 85: Individual Genes of Interest	For endpoints as specified in Section 13.1.5.	SAC				
8.12	Per Protocol	BIO_T9	Summary of Ratio to Baseline in mRNA Gene Expression Results at Day 85: Disease Signature Genes	By gene sets, gene and treatment.	SAC				
8.13	Per Protocol	BIO_T9	Summary of Ratio to Baseline in mRNA Gene Expression Results at Day 85: Lung Fibrosis Signature Genes	By gene, by treatment.	SAC				
8.14	Per Protocol	BIO_T9	Summary of Ratio to Baseline in mRNA Gene Expression Results at Day 85: Cell Module Signature Genes	By gene sets, gene and, by treatment.	SAC				
Biomarker: Tables									
-------------------	-----------------	----------------------------	--	--	---------------------------	--	--		
No.	Population	IDSL / Example Shell	Title	Programming Notes	Deliverable [Priority]				
8.15	Per Protocol	BIO_T10	Summary of mRNA Gene Signature Results		SAC				
8.16	Per Protocol	BIO_T10	Summary of the Change from Baseline in mRNA Gene Signature Results at Day 85	Page by 2GSSc and GSVA scores. This include 2GSSc, Disease, Lung Fibrosis and Cell module Signatures.	SAC				
8.17	Per Protocol	BIO_T11	Analysis of the Change from Baseline in mRNA Gene Signature Results at Day 85	Ĵ	SAC				
Joint model	of key biomar	kers							
8.18	Per Protocol	BIO_T5	Joint Model of Ratio to Baseline in Key Biomarkers at Day 85		SAC				
8.19	Per Protocol	BIO_T6	Joint Probabilities for Key Biomarkers at Day 85		SAC				
Correlation of	of Biomarkers								
8.20	Safety	BIO_T4	Correlation of Baseline Levels of Systemic Biomarkers	Baseline values only. No treatment groups. Exclude C1M results using mouse hybridoma cell line as small sample size may be unblinding. Add footnote 'Note: C1M assay changed during the study. C1M results not presented for samples analysed using the old C1M (denoted C1M*) kit due to small sample size and potential unblinding. New C1M kit denoted as C1M+.'	IA2				
Mechanistic	Haematology/	Chemistry							
8.21	Safety	SAFE_T1	Summary of Mechanistic Haematology/ Chemistry	Refer to Section 7.2 'Group 2' for	SAC				

Biomarker: Tables							
No.	Population	IDSL / Example Shell	Title	Programming Notes	Deliverable [Priority]		
8.22	Safety	SAFE_T1	Summary of Change from Baseline in Mechanistic Haematology/ Chemistry	list of endpoints	SAC		
8.23	Safety	SAFE_T1	Summary of Percentage Change from Baseline in Mechanistic Haematology/ Chemistry		SAC		

